6.2 Subject Withdrawal

Subjects may withdraw their consent to participate in the study at any time, for any reason. Investigators may also withdraw subjects from the study at their discretion in order to protect the rights, safety, or welfare of the subject. All withdrawn subjects will be included in study analyses but they will not be replaced. No missing data will be imputed.

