6.6 Treatment

The study procedure shall be performed on both eyes on the same day.

1. Eye makeup shall be removed.
2. The device shall be prepared for use in accordance with the Instructions for Use (IFU)/User Manual for the device to which the subject is randomized. An IFU/User Manual is packaged with each device that will be used in the study.

3. Anesthetic eye drops shall be instilled in both eyes.
4. Therapy shall be delivered in accordance with the IFU/User Manual for the device to which the subject is randomized.
5. For iLux device treatment, the following zones will be treated in the following order:
 - 5.1. upper lid, medial-nasal region
 - 5.2. lower lid, medial-nasal region
 - 5.3. lower lid, medial-temporal region
6. Representatives from the Sponsor may be present during the treatment but are not required.
7. Throughout the treatment visit, subjects will be assessed for any adverse events. Subjects will also be assessed for adverse events one hour following treatment, including for development of entropion or ectropion, floppy eyelids, and lash integrity assessment.
8. Following treatment, subjects will be assessed for the following:
 - Pain and discomfort using the questionnaires in Appendix C. These questionnaires must be self-assessed prior to any clinical evaluation.
 - Uncorrected Visual Acuity
 - BSCVA
 - Slit Lamp for Anterior Segment Health
 - Lid Margin Abnormalities
 - Eyelid Margin Assessment
 - Corneal Fluorescein Staining Slit Lamp Evaluation
 - Intraocular Pressure

6.7 1-Day Office Visit Follow-Up

Subjects will be required to be seen in person 1 day after the procedure for the following assessments:

- Discomfort and Pain Questionnaires (self-assessed prior to clinical evaluation)
- Uncorrected Visual Acuity
- BSCVA
- Slit Lamp for Anterior Segment Health
- Lid Margin Abnormalities
- Eyelid Margin Assessment
- Corneal Fluorescein Staining Slit Lamp Evaluation

Assessment for adverse events must include assessment for changes to eyelid margins (development of entropion or ectropion, floppy eyelids, and lash integrity assessment).

6.8 2-Week Office Visit Follow-Up

Subjects will be required to be seen in person 2 weeks (day 10-16) after the procedure for the following assessments:

- Discomfort and Pain Questionnaires (self-assessed prior to clinical evaluation)
- OSDI
- Uncorrected Visual Acuity
- Keratometry
- Manifest Refraction

- BSCVA
- Slit Lamp for Anterior Segment Health
- Lid Margin Abnormalities

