7.2.2 Secondary Effectiveness Endpoint Analysis

If the co-primary effectiveness endpoints demonstrate non-inferiority, the secondary effectiveness endpoint, change from baseline in Ocular Surface Disease Index (OSDI) at the 4-week exam, will be compared against the control device to test for non-inferiority. A similar ANCOVA model will be used to compare OSDI between devices, with covariate adjustment for baseline OSDI.

It is hypothesized that the OSDI mean score from the iLux group will not be lower than (not inferior to) the OSDI mean score from the LipiFlow group at the 4-week exam:

Null Hypothesis: $\mu (\text{iLux-OSDI} - \text{LF-OSDI}) - \delta \geq 0$

Alternate Hypothesis: $\mu (\text{iLux-OSDI} - \text{LF-OSDI}) - \delta < 0$

Where $\mu (\text{iLux-OSDI} - \text{LF-OSDI})$ = mean difference in the OSDI between iLux and LipiFlow from baseline to week 4 and $\delta = 7$.

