7.2.7 Missing Data

Primary and secondary effectiveness endpoints will be imputed when missing to preserve the randomization in the intent-to-treat analysis population. The primary method of imputation used will be by multiple imputation. Ten imputations will be produced for each endpoint using SAS PROC MI. The seed used to begin random number generation will be 11142016. The Markov chain Monte Carlo method will be used to compute with the following predictor variables: baseline tear break-up time, baseline MGS score, gender, and age. Alternate imputation methods used to assess sensitivity to the presence of missing data will be last observation carried forward (LOCF), best case (a test subject's best prior value and a predicate subject's worst prior value is imputed) and worst case (a test subject's worst prior value and a predicate subject's best prior value is imputed). If best case and worst case

conclusions differ, a tipping point analysis will be performed. In the absence of post-treatment data, baseline values will be used for imputation for alternate imputation methods.

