APPENDIX A: STUDY ASSESSMENTS

All subjects shall be assessed according to the following schedule unless otherwise specified:

Assessment	Screening	Pre-Treatment (Baseline)	Treatment	Post-Treatment	Day 1	Week 2	Week 4
Treatment Window	Day -7 to Day 0	Day 0	Day 0	Day 0	Day +1	Days 10-16	Days 21-35
Informed Consent	x						
Demographics/Medical/Ocular history	x						
Concomitant Systemic and Ophthalmic Meds	x						x
Discomfort and Pain Questionnaires		x		x	x	x	x
OSDI		x				x	x
Uncorrected Visual Acuity		x		x	x	x	x
Keratometry		x				x	x
Manifest Refraction		x				x	x
BSCVA		x		x	x	x	x
Slit Lamp for Anterior Segment Health		x		x	x	x	x
Lid Margin Abnormalities		x		x	x	x	x
Eyelid Margin Assessment		x		x*	x	x	x
Tear Break-Up Time		x				x	x
Corneal Fluorescein Staining Slit Lamp Evaluation		x		x	x	x	x
Meibomian Gland Assessment and Scoring (assess by a masked rater)		x				x	x
Intraocular Pressure		x		x		x	x
iLux OR LipiFlow Treatment per IFU/User Manual			x				
Adverse Events			x	x*	x	x	x

* 1 hour post-treatment

**APPENDIX B: OCULAR SURFACE DISEASE INDEX (OSDI)
QUESTIONNAIRE**

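### The primary multiple imputation leaves out the Week-2 MGS, TBUT and OSDI and baseline OSDI, so it ignores an observed treatment response and can favour iLux if poor responders leave that arm more often

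*Combined protocol and SAP*

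**What the plan says.** Section 7.2.7 (Missing Data) states: "Primary and secondary effectiveness endpoints will be imputed when missing to preserve the randomization in the intent-to-treat analysis population". It continues: "The primary method of imputation used will be by multiple imputation". On the details, "Ten imputations will be produced for each endpoint using SAS PROC MI", with a fixed seed, the Markov chain Monte Carlo method, and the "predictor variables: baseline tear break-up time, baseline MGS score, gender, and age". Nothing in the wording marks the list as illustrative. It contains no post-treatment value, no baseline OSDI and no treatment arm, and the section does not say that imputation is run by arm.

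The omitted values are collected. Section 6.8 opens "Subjects will be required to be seen in person 2 weeks (day 10-16) after the procedure for the following assessments", and its list includes OSDI, TBUT and the masked-rater MGS. The schedule in Appendix A agrees. Baseline OSDI is also scheduled, and Section 7.2.2 analyses OSDI "with covariate adjustment for baseline OSDI".

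The alternative methods in 7.2.7 (LOCF, best case, worst case) do use prior values, which include Week 2. A tipping-point analysis follows only if the best-case and worst-case conclusions differ.

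Section 6.2 says "All withdrawn subjects will be included in study analyses but they will not be replaced". Its next sentence rules out imputation of missing data altogether, which contradicts 7.2.7.

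**The concern.** Multiple imputation is unbiased when the variables in the imputation model account for why data are missing. If subjects leave between Weeks 2 and 4 partly because of their Week-2 result, a model without that result does not meet the condition, even though the data needed to meet it are on file. The primary analysis then uses less of the subject's own data than the sensitivity analyses do.

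Two conclusions are exposed. The first is the between-arm difference: if poor responders leave iLux more often than LipiFlow, the imputed iLux mean is too high and the lower confidence bound moves away from the margin. The second is the iLux change from baseline, which Section 7 requires to be clinically significant and different from zero before success is claimed. It is overstated whenever poor iLux responders leave, even if LipiFlow loses as many.

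For OSDI there is a further gap. The imputation model omits the covariate used in the analysis model, so imputed OSDI values are not tied to the subject's own baseline OSDI.

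**Working it through.** **Inputs from the plan.** 128 randomized 1:1, so 64 per arm (4.2); MGS margin 5 and SD 8 (7.2.4); one-tailed test (7.2.1.1). Alpha of 0.025 is stated only for the secondary endpoint.

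**Reproducing the plan's figure.** SE of the difference = 8 × √(2/64) = 1.414. Noncentrality = 5/1.414 = 3.54 on 126 df. Power at one-sided 0.025 = 93.9%, as stated. One-sided 0.05 would give 97.1%, so 0.025 is the level used. The imputation point does not affect this figure.

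**Assumed, not in the documents.**
- Week-2/Week-4 correlation ρ of 0.5 to 0.7.
- Number of leavers per arm. The plan's 10% allowance is for screening, and no later loss rate is given.
- Dropout driven by the Week-2 MGS itself.
- True MGS difference exactly −5, so any pass is false.
- Arm already in the imputation model.
- Baseline taken as uninformative about Week 4.

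**Closed form, extreme mechanism.** Suppose the lowest fraction q of an arm at Week 2 leaves. With z the q-quantile of the standard normal, the remaining subjects lie φ(z)/(1−q) SDs above the true Week-2 mean. Values imputed from them overstate the arm's Week-4 mean by SD × ρ × φ(z)/(1−q).

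| Leavers in an arm | q | z | φ(z) | φ(z)/(1−q) |
|---|---|---|---|---|
| 6 | 0.0938 | −1.318 | 0.1674 | 0.1847 |
| 4 | 0.0625 | −1.534 | 0.1230 | 0.1312 |
| 2 | 0.0312 | −1.863 | 0.0704 | 0.0727 |

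False non-inferiority rate ≈ 1 − Φ(1.96 − bias/1.414).

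- 6 iLux against 0 LipiFlow: bias = 8 × 0.5 × 0.1847 = 0.74 to 8 × 0.7 × 0.1847 = 1.03 points; rate 7.5% to 11.0%.
- 4 against 2: bias = 8 × 0.5 × (0.1312 − 0.0727) = 0.23 to 8 × 0.7 × 0.0585 = 0.33 points; rate 3.6% to 4.2%.
- Equal numbers: the two terms cancel; bias 0, rate 2.5%.

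**Simulation.** Ten proper imputations, Rubin's rules, ANCOVA with baseline, lower bound tested against −5. This also covers graded dropout, where a poorer Week-2 result raises the chance of leaving without deciding it.

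| MGS-driven dropout, ρ 0.5 to 0.7, arm modelled | Bias towards iLux | False rate, MGS alone |
|---|---|---|
| 6 vs 0, graded to extreme | about 0.2 to 1.0 | about 4% to 11% |
| 4 vs 2 | 0.06 to 0.34 | 2.1% to 5.2% |
| Equal dropout | about 0 | about nominal |
| 6 vs 0, Week 2 added | about 0 | 2.2% to 2.8% |

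A separate run set dropout by probability and took ρ up to 0.85. With 10% against 0%, or 15% against 5%, the listed predictors plus arm gave 0.47 to 0.98 points and 4.9% to 10.3%. Equal 10% dropout gave −0.03 to 0.04 points and 2.1% to 2.3%. Adding Week 2 gave −0.07 to 0.08 points and 1.9% to 3.1% across all scenarios.

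**Arm.** In that same run, fitting the list as written with no arm term gave 0.88 to 1.25 points and 7.2% to 12.2% under unequal dropout. Under equal dropout it gave 0.48 to 0.54 points and 3.2% to 3.7%. The arm term therefore belongs in the same correction.

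**Within-arm change.** When the six worst iLux subjects leave, the iLux mean change is overstated by the same 0.74 to 1.03 points whatever happens on LipiFlow. The clinical threshold in 7.1.1 is 5 points.

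**The case against.** The strongest reply is that the larger figures need a chain of conditions that the plan does not document. Treatment is given once, follow-up ends at Week 4, and nothing suggests that 9% of one arm and none of the other would leave in the last two weeks. A subject is more likely to leave over symptoms than over a gland-secretion score graded by a masked rater. If symptoms drive dropout and correlate 0.3 with MGS (also an assumption), six iLux leavers against none gives 0.02 to 0.14 points and 2.4% to 3.8%. If the six most symptomatic leave, it gives 0.21 to 0.31 points and 3.7% to 4.1%. All of this stands, and it limits confidence in the size.

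A second reply is that the sensitivity analyses would expose the problem. In simulation, LOCF contradicted 92% to 94% of false passes in the extreme case and 67% to 70% in the graded case. That is useful protection, but the primary result would still stand as reported.

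Three stronger readings are tempting and are not supported:
- A reader might infer that every leaver is scored as an average responder. The plan makes ten random draws conditional on baseline TBUT, baseline MGS, gender and age, and the point concerns only subjects with Week-2 but no Week-4 data.
- A reader might infer that the plan favours iLux whatever the dropout pattern. With arm modelled and equal dropout, the between-arm bias is about zero.
- A reader might take 11% as the trial's false-positive rate. It is for MGS alone, and Section 7.2.3 requires TBUT to succeed as well.

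**Conclusion.** The point holds as a weakness in the specified primary method. The omission is certain from the text of 7.2.7; its consequence is conditional. The between-arm bias requires loss after Week 2, dropout related to the Week-2 endpoint, and more of it on iLux. Across the assumed range the effect on MGS runs from nothing to about one point on a 5-point margin. A moderate imbalance gives about 0.1 to 0.3 points. The iLux change from baseline can be overstated even when dropout is equal. The loss rates, the dropout mechanism and the correlation are assumptions, so confidence in the size is moderate. The change is still worth making, because it removes the bias in the scenarios examined and needs no new data.

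**What to change.** In 7.2.7, extend the PROC MI model to include the Week-2 MGS, TBUT and OSDI, baseline OSDI and treatment arm (or state that imputation is run separately by arm). Keep the existing four predictors, the seed and the ten imputations. MCMC can fill a missing Week-2 value in the same run. Keep LOCF, best case, worst case and the tipping-point analysis as sensitivity analyses.

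Reconcile 7.2.7 with the statement in 6.2 that missing data are not imputed, so that one rule governs.

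The cost is a few sentences of wording and a small change to the analysis program, with no added visits, measurements or subjects. Make the change before outcome data are examined by arm, so that it cannot look data-driven.

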8 RISK ANALYSIS

Risks associated with using the iLux 2020 were assessed in accordance with ISO 14971, which is an international standard for medical device risk management that is recognized by the FDA. Most of the potential hazards identified in the analysis are common to many medical devices and are addressed by compliance with international standards. Other potential hazards unique to the iLux were addressed by assessing risk using Failure Modes Effects and Criticality Analysis (FMECA) and identifying controls to reduce residual risks to acceptable levels.

The iLux is used in the eye and the sterile disposable may come in contact with the conjunctiva and or cornea during the treatment of each lid. The sterile disposable is covered with a biocompatible silicone similar to a contact lens. There is nothing implanted either temporarily or permanently in the eye related to the iLux and the risk is similar to other meibomian gland treatments. Testing demonstrated that the disposable meets the requirements for biocompatibility (ISO 10993) and sterilization and packaging (ISO 1135, ISO 11607).

9 MEDICAL MONITOR

[name] will serve as Medical Monitor for this study to oversee the overall safety and conduct of the study. There are no formal stopping rules for this study but the Medical Monitor is responsible for notifying the Sponsor of any circumstances in which he believes the rights, safety, and/or welfare of study subjects or potential future study subjects is compromised. The Sponsor is responsible for supplying the Medical Monitor with timely, complete, and accurate accounts of all adverse events in the study as well as regular progress reports that provide information such as enrollment rate, study compliance, and/or any other issues that may impact the scientific integrity of the study. The Medical Monitor will meet periodically with the Sponsor to review study status and any issues with study conduct and/or subject safety.

10 UNSCHEDULED VISITS

Unscheduled visits will be recorded by the site and data will be collected relating to any adverse events, device-related events, or any endpoint of the study. Data will be recorded on the most appropriate CRF depending on when the unscheduled visit occurs relative to the procedure. Any unscheduled visit should not replace or be in lieu of any scheduled visit unless agreed to by the Sponsor and documented in the site regulatory file.

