4.2 Description of the Study

This study is a randomized, open-label, multisite clinical trial comparing the iLux System to an active control, which will be the LipiFlow® Thermal Pulsation System. The goal of this study is to verify that technological differences between the iLux System and the LipiFlow System do not adversely affect safety and effectiveness. The comparison between the two systems will determine if the iLux System is non-inferior to the LipiFlow System. The proposed sample size is 256 eyes (128 subjects) to demonstrate non-inferiority of treatment with iLux relative to treatment with LipiFlow for the two coprimary effectiveness endpoints. A total of 142 subjects is requested to allow for 10% fallout during patient screening. One hundred twenty-eight subjects will be randomized for bilateral treatment and will be assigned in a 1:1 ratio into the iLux treatment group or the control group at least 7 study sites.

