4.4 Outcome Measures

4.4.1 Co-Primary Effectiveness Endpoints

The co-primary effectiveness endpoints are the changes from baseline to the 4-week exam in total Meibomian Gland Score (MGS) and Tear Break-Up Time (TBUT). MGS must be assessed by a masked

¹ "Information Sheet Guidance for IRBs, Clinical Investigators, and Sponsors Significant Risk and Nonsignificant Risk Medical Device Studies", FDA CDRH, January 2006.

rater. Clinical and statistically significant improvements from baseline for each parameter are required to achieve success for these co-primary endpoints.

The MGS is determined for the lower eyelids using a device that applies a standardized pressure to an area including 5 glands (Meibomian Gland Evaluator, Model MGE-1000, TearScience, Inc.) while viewing the eyelid margin using a slit lamp microscope to determine the presence and quality of the gland secretions. A total of 15 glands in three lower eyelid zones (nasal, medial, temporal) will be evaluated. Each gland is graded from 0 to 3 (0 = no secretion, 1 = inspissated, 2 = cloudy, 3 = clear liquid). The maximum MGS score is 45 in each eye. This endpoint has been used in previous studies evaluating the LipiFlow device [5, 6]. The clinician performing the MGS must not be involved in the study procedure and must be blinded to which arm of the study the subject is randomized.

TBUT is evaluated using the fluorescein method [4]. This measurement provides an aggregate assessment of the effectiveness of treatments to both the lower and upper eyelids.

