13 STUDY MONITORING REQUIREMENTS

It is the responsibility of the study Sponsor to ensure proper monitoring of the investigation and to see that all the clinical requirements are met. Either sponsor personnel or a contracted third party will perform monitoring. In general, monitoring will consist of an initiation visit to train the site on the proper use of the device and execution of the protocol. Ongoing monitoring will consist of periodic visits to the site to compare study eCRF data with site source data. The frequency of these visits will depend on site enrollment and observations during prior visits. During monitoring visits, the monitor may review the subject records to verify that all records and files are current and to assure compliance with all requirements of this protocol as well as with applicable IDE regulations. The final monitoring visit may also serve as the study close-out visit.

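### Section 10 lets the sponsor of an open-label trial agree to substitute an unscheduled visit, and no rule fixes which measurement is the Week-4 co-primary value

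*Combined protocol and SAP*

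**What the plan says.** Section 10 sets three rules for unscheduled visits.

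- Endpoint data are taken at them: "data will be collected relating to any adverse events, device-related events, or any endpoint of the study".
- The form is chosen by timing: "Data will be recorded on the most appropriate CRF depending on when the unscheduled visit occurs relative to the procedure".
- Replacing a scheduled visit is barred, with one exception: "Any unscheduled visit should not replace or be in lieu of any scheduled visit unless agreed to by the Sponsor". The exception in full reads "unless agreed to by the Sponsor and documented in the site regulatory file".

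The setting is given elsewhere. Section 4.2 states: "This study is a randomized, open-label, multisite clinical trial comparing the iLux System to an active control". On MGS, Section 4.4.1 says: "The clinician performing the MGS must not be involved in the study procedure and must be blinded to which arm"; Table 1 in Section 6.4 repeats this for the assessment itself. On TBUT, Section 4.4.1 says only "TBUT is evaluated using the fluorescein method [4]" and adds nothing about who measures it or whether that person knows the arm. Section 13 says of oversight: "Either sponsor personnel or a contracted third party will perform monitoring". That work includes comparing eCRF entries with source data while the trial runs. No masking of the sponsor is stated.

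The Synopsis and Appendix A place the Week-4 visit in Days 21-35. Sections 7 to 7.2.7 define the analysis as change from baseline to Week 4. They do not say which measurement is used if a subject has more than one, or if the only one comes from an unscheduled visit.

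**The concern.** Section 10 gives no criteria for the sponsor's agreement. It does not require the decision to precede the results, and it names no independent or masked decision-maker. In an open-label trial the sponsor can know the arm, and through monitoring it may know the values. If two assessments exist for a subject, the plan has no rule that settles the choice between them.

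Choosing between measurements with arm and result in view is outcome selection. If it favoured iLux, the estimated difference would move toward non-inferiority and the one-sided error at the margin would exceed its nominal level. A masked MGS rater protects each score but not a later choice between two properly masked scores. TBUT has neither protection on paper.

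The same gap reaches the sensitivity analyses. The best-case and worst-case imputations in Section 7.2.7 draw on a subject's best or worst prior value, and the plan does not say whether unscheduled values count.

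**Working it through.** **Inputs from the documents**
- Sections 4.2 and 7.2.4: 128 subjects, 1:1, so 64 per arm.
- Section 7.2.4: MGS margin 5, SD 8; TBUT margin 2.5 s, SD 4 s; stated power 93.9% each and 88.2% jointly.
- One-sided alpha 0.025. Section 7.2.4 states this only for OSDI; I assume it for the co-primaries.

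**Reproducing the plan's figure**
- MGS standard error = 8 x sqrt(2/64) = 1.414, so margin/SE = 5/1.414 = 3.54.
- Normal approximation: Phi(3.54 - 1.96) = 94.2%. Noncentral t with 126 df: 93.9%, as stated. TBUT has the same margin/SD ratio (0.625) and so the same power.
- Joint power under independence: 0.939^2 = 88.2%, as stated.
- One-sided 0.05 would give 97.1%, which does not match, so 0.025 is what the plan used.

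The planned size therefore stands. The question is bias and error rate.

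**Illustration of the opening**

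Assumptions, none of them in the documents: a fraction f of iLux subjects have two assessments and the better one is kept; LipiFlow values are left alone; the two assessments correlate at rho between 0.5 and 0.9.

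- Mean gain in an affected subject = SD x sqrt((1 - rho)/pi). For MGS this is 8 x sqrt(0.5/pi) = 3.19 at rho 0.5 and 8 x sqrt(0.1/pi) = 1.43 at rho 0.9.
- Bias in the arm difference = f x gain.
- Error at the margin = Phi(bias/SE - 1.96).

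| f | iLux subjects (of 64) | MGS bias, points | Per-endpoint error |
|---|---|---|---|
| 2% | about 1 | 0.029-0.064 | 0.026-0.028 |
| 5% | about 3 | 0.071-0.160 | 0.028-0.032 |
| 10% | about 6 | 0.143-0.319 | 0.032-0.041 |
| 20% | about 13 | 0.285-0.638 | 0.039-0.066 |

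For TBUT the biases are half as large in seconds (for example 0.071-0.160 s at 10%), and the error rates are the same because SD and SE both halve. If the worse of two values were also kept in the same fraction of LipiFlow subjects, 10% would give 0.039-0.066. A simulation of 20,000 trials per setting gave 0.026-0.032 at 5% and 0.030-0.040 at 10% in the iLux-only case, which agrees with the formula.

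**Trial-level meaning**

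Section 7.2.3 requires both co-primaries to succeed. Section 7 also requires a clinically significant change from baseline in the iLux arm. The per-endpoint figures are therefore upper bounds on the trial's false-success rate in each scenario.

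**What happens to values declared missing**

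The imputation predictors listed in Section 7.2.7 are baseline TBUT, baseline MGS, gender and age; arm is not among them. Suppose the model is run as listed with arms pooled, the true deficit is 5 points, and 10% of iLux values are missing. Then 57.6 iLux and 64 LipiFlow values are observed, and the pooled mean lies 5 x 64/121.6 = 2.63 points above the iLux mean. The iLux mean shifts by 0.10 x 2.63 = 0.26 points, inside the 0.143-0.319 range for selection in 10% of subjects. A remedy that simply discards usable values could bring in as much bias as it removes.

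**The case against.** The strongest reply is that the rule is a prohibition with a documented exception. Filing the agreement leaves an audit trail, and the natural use of the exception is a subject who could attend only at another time, which yields one measurement and no choice. Better-of-two selection needs two full assessments, sight of both results, and then a choice. No section says the sponsor sees values before agreeing, and a third party may do the monitoring. This stands as a limit on weight: the clause creates an opportunity, and the documents do not describe a practice. An audit trail shows a substitution afterwards but does not prevent it.

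Three stronger readings are tempting, and the documents do not support them.

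- A reader might infer that an unscheduled MGS need not be masked. Section 4.4.1 and Table 1 require a masked rater with no limit to scheduled visits; Section 10 merely does not repeat it.
- A reader might infer that sponsor agreement waives the window. Section 10 does not say so, and Days 21-35 are stated in the Synopsis and Appendix A. What is missing is an explicit link between substitution and the window.
- A reader might infer that unscheduled values overwrite scheduled ones on the form. Section 10 assigns the form by timing and says nothing about overwriting.

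The size is also open to challenge, since frequency, repeat correlation and one-directional use are all assumed. At 2% the inflation is negligible, and 10% would mean about six iLux subjects with a second full assessment and a favourable choice each time. I accept that, and I use the figures only to show scale.

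**Conclusion.** The concern holds as a gap in pre-specification. An interested and unmasked party may approve substitution without criteria, and the analysis section has no rule for the Week-4 value. TBUT is the more exposed co-primary; MGS is exposed only through the choice between visits.

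The likely effect is small: error of 0.026-0.028 per endpoint at 2% of iLux subjects and 0.032-0.041 at 10%, against a nominal 0.025. This rests on the better of two values being kept in iLux only, repeat correlation of 0.5-0.9, and one-sided alpha of 0.025 for the co-primaries. The documents do not support a claim that the sponsor intends to select values, or that the error rate is in fact inflated. The change is still worth making because it is nearly free and removes a question that could not be settled after unblinded data exist. Sample size and the stated 93.9% power per endpoint are unaffected.

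**What to change.** Replace sponsor discretion for the effectiveness endpoints with a fixed rule in Section 10 and Section 7, applied identically in both arms:

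- The Week-4 value is the first complete assessment within Days 21-35, with MGS by the masked rater, whether the visit was labelled scheduled or unscheduled. Define complete, for instance as both co-primary measures in both eyes.
- Any exception is decided and documented by someone masked to arm and to the values.
- Substitutions are listed by arm, and a sensitivity analysis excludes them.
- A subject with no in-window assessment has a missing Week-4 value. Before relying on this, reconcile Section 6.2, which rules out imputation, with Section 7.2.7, which prescribes it, and add treatment arm to the imputation model.
- State whether unscheduled values count as prior values in the Section 7.2.7 sensitivity imputations.

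Unscheduled-visit data remain in use for safety as now. An outright ban on unscheduled visits for effectiveness would be worse, because it would discard usable in-window data and send them to imputation.

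Cost: protocol and analysis wording, one extra sensitivity analysis, and possibly a few more missing Week-4 values when a subject can attend only outside the window. Sample size does not change.
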